14.1 Study Overview

Adolescents will be screened and enrolled in the study and randomized in a blinded manner to either the active treatment or sham treatment group. Neither the subjects nor the investigators will know whether the treatments are active or sham in nature. All subjects will have baseline mood, safety, and cognitive assessments. Subjects at sites conducting the Structural Head MRI subset will have baseline imaging. All subjects will then undergo 30 TMS treatments within the 6 week timeframe. Mood, safety, and cognitive assessments will be performed at regular intervals throughout the study (see Appendix A for schedule of events). After the final treatment (i.e., treatment #30 or at early withdrawal), the mood and cognitive assessments will be performed for all subjects.

The treatment and assessment schedules for Phase I are identical for both the active and the sham treatment cohorts. For subjects in the Structural MRI subset, MRI scans will also occur after the final treatment for Phases I and II and again at the 6-month follow-up visit.

14.2 Subject Compliance Monitoring

Non-adherence to the assigned treatment regimen is defined as missing ≥ 3 treatments in daily sequence, or missing more than 20% of the total number of treatment sessions occurring during the 6 weeks of acute treatment (does not include taper treatments) as outlined in the schedule of events (i.e., 100% compliance = 30 total treatments). However, if the subject does miss a treatment, the subject must not go more than 3 calendar days without a treatment session. Treatments missed during the taper visits are considered protocol deviations. Subjects who are unable to comply with this schedule may be withdrawn from the investigational treatment portion of the study. If a subject receives more than the prescribed number of pulses (i.e. 3000 pulses of good contact), this would be considered an overdose and documented on the SAE form and reported to Neuronetics.

14.3 Prior and Concomitant Therapy

Reasonable efforts will be made to determine all somatic therapies for depression received by the subject in the past 2 years. All other medications and therapies received within six months of study enrollment will also be determined. All relevant information will be recorded on the subjects CRF. The ATR will be used in this study to verify the inclusion criteria pertaining to treatment resistance and intolerance. (See Study Reference Manual for details of the administration of the ATR.)

Permitted Concomitant Therapy

Zaleplon, zolpidem, or zopiclone (1 dose nightly) as needed for treatment emergent insomnia or lorazepam (up to 2 mg daily) for treatment emergent anxiety, may be administered for up to 14 doses during Phase I and an additional 14 doses during Phase II. For Phase III, these medications may be administered for up to 10 days, on \leq 5 occasions. The use of alternative hypnotics or anxiolytic compounds requires prior approval from the Sponsor. Hormonal contraceptives are allowed if the subject has been on a stable dose for at least 3 months. Short-term treatments for headaches, allergies, colds, and flu symptoms will be allowed during the study provided the medications utilized have no established psychotropic effects that would be expected to confound interpretation of study outcome measures. These medications may include non-sedating, over-the-counter, or prescription antihistamines, analgesics and decongestants. All questions regarding the acceptability of specific medications must be approved by the Sponsor.

[figure not shown]
Page 37 of 61

CONFIDENTIAL

Prohibited Concomitant Therapy

Any medication administered for the treatment of any psychiatric or neurologic disorder or any other known CNS active drugs, including herbal, over-the-counter, and homeopathic medications, MAOIs, other antidepressants, antipsychotics, stimulants and mood stabilizers are prohibited during this study (See Appendix D, Concomitant Medication Exclusion List). Use of Zaleplon, zolpidem, zopiclone or lorazepam for more than the permitted days (see above) or beginning a new regimen of hormonal contraception may lead to excluding the subject from the study.

14.4 Phases – Randomized, Triple-Blinded

15 Statistical Plan

15.1 Sample Size and Power Calculation

There are no large, randomized controlled trials of the use of transcranial magnetic stimulation (TMS) in the treatment of adolescent major depressive disorder that can be used to estimate effect size. Therefore, several different sources of evidence were used to estimate the expected effect size of treatment as proposed in this protocol. First, evidence was reviewed from the study by Wall and colleagues, who reported preliminary data from a small patient population of adolescents treated with the NeuroStar TMS Therapy System in an open label study design (Wall, 2011). This study is especially relevant because it is the only available evidence using the specific TMS device (i.e., the NeuroStar TMS Therapy System) that will be utilized in the NeuroStar TMS Adolescent MDD RCT, and it used the identical stimulation parameters and duration of treatment proposed in this study protocol. In that report, eight adolescent patients participated who had previously failed to benefit from treatment with 2 or more antidepressant medications and were currently in stable treatment with a single ineffective (selective serotonin reuptake inhibitor, SSRI) antidepressant medication. Seven of 8 patients, ages 14-18 years, completed all 30 treatments in this study. The primary outcome measure was the Children's Depression Rating Scale-Revised (CDRS-R) which showed significant improvement from baseline (mean [SD]) (69.6 [6.6]) at treatment 10 (50.9 [12]), P<0.02, treatment 20 (40.1 [14]), P<0.01, treatment 30 (32.6 [7.3]), P<0.0001, and at 6-month follow up (32.7 [3.8]), P<0.0001.

Using this data, the mean change in CDRS-R total score was estimated to be approximately 33, with a standard deviation of 7.3. It is presumed that a treatment difference of 8.0 points on the CDRS-R scale between randomized treatment conditions may be anticipated in a sham-controlled study, and that a conservative estimate for a pooled standard deviation is 10.0 points, which results in an estimated standardized effect size of 0.80. This is considered to be the upper bound of an expected magnitude of treatment benefit in an adolescent depression study population. Under these assumptions, it is presumed

that a sample size of approximately N=35 patients per treatment group, with an alpha level = 0.05 would provide approximately 90% power to detect a treatment difference between active and sham TMS groups.

Another important source of evidence to consider in estimating an effect size for this study can be derived from randomized controlled trial evidence from the study of antidepressant medications that are FDA approved as treatments for adolescent patients with major depressive disorder. The relevant medications to consider include the medications fluoxetine (Emslie, et al., 1997; 2002) and escitalopram (Emslie, et al., 2007). Replicated studies of the antidepressant fluoxetine have shown active versus sham treatment differences using the CDRS-R that range from approximately 7 to 9 points, with associated pooled standard deviations of approximately 9 to 12 points. Estimated standardized effect sizes in these studies are reported as moderately large, approximately 0.50 (Emslie, et al., 1997; 2002). Results of similarly designed studies of escitalopram suggest a lower estimated standardized effect size of approximately 0.30 (Emslie, et al., 2009).

In addition to these data, the results of a large, federally-supported multisite study of the use of antidepressant medication for the treatment of adolescent major depression are also relevant to consider. This study was not specifically directed at the question of antidepressant medication monotherapy alone, rather the design was intended to examine the effectiveness of the combination of antidepressant medication alone treatment condition in this study provides important supportive information in an estimation of the anticipated standardized effect size in adolescents. The Treatment of Adolescent Depression Study (TADS) (March, et al., 2004) examined the benefit of the use of fluoxetine alone, CBT alone, or the combination of the two versus a placebo condition. In that report, the use of fluoxetine alone versus placebo was observed to demonstrate a standardized effect size of 0.68, similar in magnitude to the results of the Emslie and colleagues studies described above (Emslie, et al, 1997; 2002). It should be noted, however, that these studies with antidepressant medication utilized a treatment-naïve study population, excluding patients with treatment resistant depression.

Based on the aggregate evidence described here, it is anticipate that this study, if effective in demonstrating the superiority of NeuroStar TMS Therapy[®] compared to sham TMS in adolescent patients with treatment resistant major depressive disorder, may be expected to demonstrate a standardized effect size of approximately 0.50 to 0.60. As a stand-alone analysis, it is therefore expected that a sample size of 50 patients per treatment arm, at an alpha level of 0.05, should provide greater than 85% power to detect a statistically significant difference between the treatment groups. However, as noted further below, efficacy also may be established by analysis of the adolescent study data using a frequentist approach which borrows data from two prior adult RCTs in major depression using the NeuroStar TMS Therapy System.

15.2 Analysis Plan

This study in adolescent patients is a randomized, parallel-group comparison of treatment with TMS as compared to a sham control. It will be conducted at approximately 16 sites in the United States and Canada, with independent randomization protocols within each site, using a permuted block design to improve balance within site. The primary outcome is the last post-treatment symptom score (LV) measured using the primary efficacy outcome measure (efficacy variable and point of declaration are blinded to the Investigator) for each subject. The analysis will be performed on the strict intention-to-treat sample of all evaluable subjects, meaning those subjects with a baseline and at least one post-baseline observation available for analysis.

Page 40 of 61

Poorly recruiting sites, defined as those with fewer than 2 randomization blocks, will be pooled into one or more pseudo-sites for purposes of analysis. To ensure that nearly all sites will be of adequate size we will adopt a strict closure policy for sites that do not show early signs of enrollment success. With 16 sites, the average number of subjects per site is approximately 18, so there may be a few sites with fewer than 2 randomization blocks. A site that has not randomized at least 2 subjects in the first quarter of their enrollment may be closed. Then if as many as 2 sites are closed, and one poorly performing site eludes closure, there will be no more than one pseudo-site comprising a total of no more than 2 subjects from the closed site and approximately 11 from the poorly performing site, or no more than 13 subjects in all (i.e. <5% of the total sample).

As noted elsewhere in this protocol, the sites will remain blinded to which efficacy measure has been declared as the primary outcome and to the point of efficacy declaration in order to improve the study's signal detection ability. Point of declaration and the primary outcome measure will be documented in the study master file prior to unblinding of the dataset. The null hypothesis will be tested in an analysis of covariance of the LV, using baseline score, and ATR medication resistance level as fixed effect covariates, adjusting for site differences using a random effect. As discussed elsewhere, the ATR medication resistance levels will group subjects categorically by number of medications which have shown an adequate degree of resistance for that subject. These resistance levels will be grouped into two categories in statistical model, 0-1 in the current episode or 2-4 in the current episode, unless the final distribution of ATR scores in the study population suggests another allocation would be more statistically appropriate. All tests are two-sided, at the 5% level. The primary outcome should be available and meaningful for nearly all subjects, so the main analysis will be by strict intention-to-treat as defined above. An analysis of observed cases only will be performed as a secondary outcome measure. A site by treatment interaction analysis will be done as a secondary analysis to see if there is significant heterogeneity in the effect of TMS across sites. In particular, we will examine site-specific treatment effects (with confidence intervals) to test for evidence of true reversal of effect.

Secondary outcomes include other continuous measures, and within-subject dichotomous variables as outlined in the efficacy variables described elsewhere in this protocol. The treatment effect null hypothesis will be tested by logistic regression on treatment group assignment with adjustment for site and ATR medication resistance level. In addition, the longitudinal symptom scores will be analyzed with a general linear model adjusting for baseline scores and ATR medication resistance level, using a saturated means model for time since baseline, with treatment effect parameterized by a linear effect in time. The correlation of scores within individuals over time will be handled by allowing a within-subjects residual covariance matrix selected by exploration of the sample semi-variogram, as described by Diggle, Liang and Zeger. If this exploration reveals that a mixed model approach will fit the covariance structure better, random effects will be included in the model. As in the main analysis, site by treatment interactions will be tested.

In addition to testing the hypothesis noted above in the study alone, a meta-analysis will be used to establish evidence of efficacy. Specifically, in addition to the evidence to be obtained in this study protocol, there are already two large, randomized, multisite sham-controlled studies of the use of the NeuroStar TMS Therapy[®] System in adult patients (ages 18-70 years of age) with major depressive disorder. These data are statistically important to consider in the interpretation of the data to be collected in the adolescent study population using the NeuroStar[®] TMS device. Therefore, a frequentist analysis will be used to demonstrate the effectiveness of the NeuroStar TMS Therapy System across ages 12-70 by borrowing data from the two adult studies to be used in a meta-analysis with the adolescent study data. This approach effectively allows meaningful computational use of the preponderamce of adult study evidence with the adolescent study datato permit a "sample-sparing" adolescent study design. This approach is clinically justified by the substantial evidence of safety and effectiveness already shown in the adult patient population, the biological and clinical continuity of the disease state from adolescence to

adulthood, the shared mechanism of action of transcranial magnetic stimulation across age groups, and because of the significant unmet need in treatment options available for adolescent patients with major depressive disorder.

Details of the statistical approach to be used in the meta-analysis are contained in the blinded statistical plan associated with this study protocol. The meta-analysis will include data from all three studies. The model for this analysis will include the following terms: treatment (active vs. sham), baseline score (continuous), medication resistance level as determined using the Antidepressant Treatment Record (ATR), (ATR=1 'Lo' vs. ATR=2-4 'Hi'), and Study (adolescent study (IDE G120121), and the two adult studies combined (O'Reardon, et al, 2007 and George, et al, 2010) as fixed effects, and, interaction terms for "study-by-treatment" and "ATR medication resistance level-by-treatment". A random effect of "site nested within study" will also be included to assess any potential site effects.

Based on this meta-analysis, there are 3 essential criteria to declare success and conclude that the evidence rejects the null hypothesis of no difference between active TMS and sham TMS in adolescent patients with treatment resistant major depressive disorder. These criteria are:

- 1) The main effect of treatment on the primary efficacy variable of mean change from baseline on the HAMD24 in the adolescent/adult studies meta-analysis will be statistically significant, and fall below the specified alpha level of 0.05,
- There will be no statistically significant evidence of interaction between Study and Treatment on the primary efficacy outcome variable at the pre-specified alpha level > 0.10,
- 3) The study-specific treatment effect observed for the primary efficacy outcome variable in the adolescent study as a stand-alone analysis will reside between the ranges of 1.7 points to 5.5 points on the HAMD24, and to meet the maximum Type I error rate of 15%.

The criteria above are clinically justified based on the results using the HAMD24 outcome measure in the prior adult studies which ranges from 1.7 to 2.5 (O'Reardon, et al, 2007; George, et al, 2010). The maximum Type I error rate of 15% for the adolescent data alone is justified given the large dataset available in adults (N=491) and that adult and adolescent populations should respond similarly to TMS Therapy. Simulations using data from the adult studies and N=100 adolescents, shows that with a type I error rate of 5%, the observed HAMD24 mean difference between active and sham treatment would need to be 2.67, which would require a result greater than what it would need to achieve had it been considered alone. For this reason, the 15% type I error rate for the adolescent data is justified.

If the criteria described above for pooling the adolescent study with the adult studies are not satisfied, the adolescent study must stand alone. If the results of the analysis of the adolescent study shows a statistically significant treatment group difference in favor of the active treatment at a pre-specified alpha level = 0.05, then this study alone will be sufficient to establish efficacy in the adolescent population.

A listing of the efficacy outcome measures and their intended sequence of testing in priority order are listed here. Note that the point of declaration of efficacy for the primary outcome measure is concealed from the Investigator and hence, is not specifically noted in this listing. All tests are to be performed on the intent to treat sample unless specifically noted. Please refer to the Schedule of Events for a listing of study timing for collection of primary and secondary outcome measures.

Primary Efficacy Outcome Measure	Definitions
HAMD24: total score, intent to treat	HAMD24 total score change from baseline value [Blinded
sample using last post-treatment score	point of declaration of efficacy for primary outcome
	measure included in statistical supplement]
Secondary Efficacy Outcome	
Measures	
Continuous outcomes	[Blinded point of declaration of efficacy for secondary
HAMD17, MADRS, CDRS-R, QIDS-	outcome measures included in statistical supplement]
A17-R, CGI-S: total score, intent to treat	
sample using last post-treatment score	
Responder categorical outcome	
HAMD (24 and 17 Item versions)	For HAMD, MADRS, CDRS-R, and QIDS-A17-SR:
MADRS	proportion of patient population achieving an end of acute
CDRS-R	phase total score reduction of \geq 50% compared to baseline
QIDS-A17-SR	score
CGI-S	For CGI-S: End of acute treatment score of 1,2 or 3.
Factor scores derived from the HAMD	
including (using the last post-treatment	
value)	
Anxiety/Somatization	Anxiety/Somatization (sum of items 10, 11, 12, 13, 15, 17)
Core Factor	Core Factor (sum of items 1, 2, 3, 7, 8)
Maier	Maier (sum of items 1, 2, 7, 8, 9, 10)
Gibbons	Gibbons (sum of items 1, 2, 3, 7, 9, 10, 11, 14)
Retardation	Retardation (sum of items 1, 7, 8, 14)
Sleep	Sleep (sum of items 4, 5, 6)
Remitter categorical outcome	
HAMD (24 and 17 Item versions)	For HAMD24: End of acute treatment score < 11
MADRS	For HAMD17: End of acute treatment score < 8
CDRS-R	For MADRS: End of acute treatment score < 10
CGI-S	For CDRS-R: End of acute treatment total score < 28
	For CGI-S: End of acute treatment score 1 or 2

Table 4. Prioritized Order of Testing of Primary and Secondary Outcome Measures

1

The integrity of the masking of the efficacy treatment conditions will be evaluated by exploratory analyses of the efficacy measures with subjects grouped by prominent self-reported spontaneous adverse events. In addition, subjects and Parents will complete a Pre/Post-Treatment Expectations and Experience Questionnaire (PRE-TEEQ-A/PRE-TEEQ-P and POST-TEEQ-A/POST-TEEQ-P) that queries their initial expectations of trial outcome and final impression of the trial.

Neurocognitive safety outcome measures will be compared from end of each phase to Phase I baseline and previous phase completion assessments.

16 Safety and Adverse Events

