10.2 Efficacy and Safety Assessments

Phase I

See Appendix A for schedule of events.

Outcome Assessments

Trained physicians and raters will administer all diagnostic assessments and clinical interviews determining study eligibility during screening and prior to randomization. All study staff will be trained on study procedures by Neuronetics staff.

Outcome screening will occur after both the Informed Assent/Consent Document and the HIPAA Authorization are signed. Baseline assessments will occur prior to the first TMS treatment session. Outcome measures in Phase I will be assessed at the end of treatment weeks 4 and 6. The following outcome assessments will be completed: HAMD/MADRS structured interview, CDRS-R, CGI-S, and QIDS-A17-SR.

Safety Assessments

A physical and complete medical and psychiatric history will be obtained at the screening visit.

Page 26 of 61

Vital signs including height, weight, blood pressure and heart rate will be collected at the baseline visit and at week 6.

Laboratory determination will be measured at screening and include: Blood chemistry, hematology, urine drug screen, and urine pregnancy for female subjects.

Subjects will be evaluated clinically for adverse events at each visit. Serious adverse events (SAEs) will be recorded as they occur and reported to Neuronetics by the study site within one business day of notification.

Cognitive function assessments will be conducted at the baseline visit and at week 6. The following tests from the NIH Toolbox Cognition Battery are used for this study:

- Education
- Handedness
- Attention
 - o Flanker Inhibitory Control and Attention Test
- Episodic Memory
 - Picture Sequence Memory Test
 - Auditory Verbal Learning Test (Rey)
- Executive Function
 - Dimensional Change Card Sort Test
 - Flanker Inhibitory Control and Attention Test
- Language
 - Picture Vocabulary Test
 - Oral Reading Recognition Test
- Processing Speed
 - Pattern Comparison Processing Speed Test
- Memory
 - List Sorting Working Memory Test

The C-SSRS will be completed weekly during TMS treatment to assess worsening of illness and suicidality. The YMRS will be completed at baseline and will be repeated based on reported change in symptoms.

Air conduction thresholds will be assessed for both left and right ears at the baseline visit and at week 6.

Phase II

See Appendix B for schedule of events. The schedule of efficacy and safety measures for Phase II will be identical to that of Phase I.

Phase III

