Appendix A. Phase I Schedule of Events

a. A minimum of 7 days may elapse between the screening and baseline visits; a maximum of 5 days may elapse between the baseline visit and the first treatment day of Week 1. All baseline assessments must be completed and laboratory results received before 1st TMS treatment.

b. The first visit during each week of treatment should occur on a Monday, with daily treatment sessions occurring on Monday through Friday of each week.

c. Subjects who prematurely discontinue should complete all Week 6 procedures within 2 days after their last TMS treatment session.

d. If subject <18 yrs of age or the legal age requirement of the state

e. Efficacy, neuropsychological and safety assessments to be performed after last TMS treatment session on last day of the treatment week when assessments are required. Y-MRS to be completed if symptom indicating mania occurs. If positive, a M.I.N.I./M.I.N.I. KID must be repeated to determine if subject meets full DSM-5 criteria for mania or hypomania. If positive, subject to be discontinued from the study and followed clinically.

f. Subject must have been off of any antidepressants for at least one week.

g. Laboratory determinations to include standard hematology, and blood chemistry.

h. If subject is female of childbearing potential, a urine pregnancy test will be performed in the office at screening.

i. Performed on a subset of subjects at participating sites,

j. Adverse events occurring prior to randomization will be recorded as part of each patient's medical history. Those AEs occurring following the first TMS treatment session through 30 days after last study visit will be collected.

Page 53 of 61

k. Medication treatment for emergent insomnia and emergent anxiety is permitted (refer to protocol for usage allowance). Refer to Appendix D for the Concomitant Medication List.

I. In addition to the indicated day, Motor Threshold Determination (MT) may be repeated at any time during the course of the active TMS treatment sessions based on clinical assessment of the supervising physician. Justification for the additional MT must be documented and pre-approved by the Sponsor when possible.

m. Taper occurs only if exiting the study or transitioning directly to Phase III.

Page 54 of 61

CONFIDENTIAL

Phase		6-Week Open Label Acute Treatment					3-Week Post-Treatment Taper ⁱ			
Week	Wk 1 ^b	Wk 1 ^b Wk 2 ^b Wk 3 ^b Wk 4 ^b Wk 5 ^b Wk 6 ^{b,c} /ET							Wk 3	

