## G. Cognitive Function Testing:

Cognitive testing will be conducted using the NIH Toolbox. All sites are provided with the NIH Toolbox recommended computer set-up, and are trained on the specific procedures for implementation of the measures to be use in this study. Specifically, eight tests contained within the NIH Toolbox Cognition domain are being obtained in subjects at up to 4 time points in the study (please see the Schedule of Events elsewhere in this document for the specified time points of NIH Toolbox administration).

44-02219-204, Rev C 21-JAN-2019

Page 22 of 28

Data output from the NIH Toolbox are summarized for each test in Table 4 above, and includes Computed Score or Raw Score, Age-Adjusted Scale Score, Fully-Adjusted Scale Score, and Age-Adjusted National Percentile. Data output is extracted from the NIH Toolbox website.

Cognitive Function values are measured at baseline prior to treatment, at the end of each phase, and include the measures listed in Table 4. During the study, the test was moved from a desktop version to an IPAD tablet based version. There were slight changes in the test but both versions contained the same test battery elements.

|--|

Variable Name	Туре	Items
Episodic Memory	- 190	
Auditory Verbal Learning Test (Rey)	Continuous	Raw Score
	~ .	Mean, SD, Median, Range
Picture Sequence Memory Test	Continuous	Computed Score(Age-Adjusted Scale Score) Fully-Adjusted Scale Score
		Age-Adjusted National Percentile
		Mean, SD
		Median, Range
Working Memory	a i	
List Sorting Working Memory Test	Continuous	Raw Score (Age-Adjusted Scale Score), Fully-Adjusted Scale Score
		Age-Adjusted National Percentile
		Mean, SD,
		Median, Range
Executive Function Dimensional Change Card Sort Test	Continuous	Computed Score(Age-Adjusted Scale Score)
Dimensional Change Card Soft Test	Continuous	Fully-Adjusted Scale Score
		Age-Adjusted National Percentile
		Mean, SD
Flanker Inhibitory Control and	Continuous	Median, Range Computed Score(Age-Adjusted Scale Score)
Attention Test	Continuous	Fully-Adjusted Scale Score
		Age-Adjusted National Percentile
		Mean, SD
		Median, Range
Processing Speed Pattern Comparison Processing	Continuous	Raw Score (Age-Adjusted Scale Score),
Speed Test	Continuous	Fully-Adjusted Scale Score
1		Age-Adjusted National Percentile
		Mean, SD,
Language		Median, Range
Oral Reading Recognition Test	Continuous	Computed Score(Age-Adjusted Scale Score)
		Fully-Adjusted Scale Score
		Age-Adjusted National Percentile
		Mean, SD

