## J. Auditory Threshold Testing:

Air conduction auditory threshold is obtained at baseline, and repeated up to 3 additional time points in the study depending upon the subject's participation in the various study phases (see Schedule of Events above). Air conduction threshold results are reported as means of right and left dB readings for each of the 8 specified test frequencies across the baseline and end of study phase time points, and the change in dB readings from baseline at the end of study phase time points, using a standard audiogram format and summarizing by study group.

For each of the 8 specified test frequencies both the observed outcome and the change from baseline to end of study phase will be summarized (using the standard audiogram format as noted above). The treatment groups will be compared with respect to the baseline outcome and the change from baseline to end of study phase. The null hypothesis of the equality of the treatment group means will be tested using a t-test. Within each treatment group the statistical significance of the mean change from baseline to end of study phase will be assessed using a paired t-test. For each treatment group the data will be summarized showing the sample size, mean, median, standard deviation, minimum, and maximum.

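### No active-sham comparison of the cognitive safety tests is pre-specified for Phase I; the only stated comparison is with the subject's own earlier scores

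*Protocol*

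**What the plan says.** The protocol's analysis of cognition is a single sentence in 15.2: "Neurocognitive safety outcome measures will be compared from end of each phase to Phase I baseline and previous phase completion assessments". Both comparators are earlier scores of the same subjects.

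SAP 8.G says "Cognitive Function values are measured at baseline prior to treatment, at the end of each phase, and include the measures listed in Table 4". It then lists, for each test, the scores to be extracted and the mean, SD, median and range. Its running text names no group contrast, model, estimate or confidence interval.

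On timing, Protocol 10.2 says of Phase I "Cognitive function assessments will be conducted at the baseline visit and at week 6". Appendix A, footnote a, places baseline before any treatment: "a maximum of 5 days may elapse between the baseline visit and the first treatment day of Week 1". Footnote e places the later test after a session: "Efficacy, neuropsychological and safety assessments to be performed after last TMS treatment session on last day of the treatment week when assessments are required". SAP 8.G also records that the battery moved from a desktop to a tablet version during the study, with slight changes to the test. It gives no adjustment for this.

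Other safety measures are treated differently. For hearing, SAP 8.J says "The treatment groups will be compared with respect to the baseline outcome and the change from baseline to end of study phase" and specifies a t-test. SAP 8.E tabulates the C-SSRS by active and sham condition.

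**The concern.** Phase I is randomised 1:1 against sham (SAP 1.A), and both arms follow the same assessment schedule (Protocol 14.1). Protocol 9.1 makes safety part of the primary objective of a sham-controlled study, and 9.2 lists acute safety as a secondary objective. Yet for cognition the stated comparison does not use the control arm.

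A subject's change from baseline to Week 6 on memory, speed and executive tests contains more than any effect of stimulation:

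- gain from taking the same tests a second time;
- non-specific effects of being tested after a 37.5-minute session, when baseline was not;
- for some subjects, a change of test platform between the two visits.

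All of these arise in both arms. A retest gain can offset a real loss, so that no decline is reported. A non-specific post-session dip can look like harm. If the contrast with sham is not pre-specified, whether and how to report it may be decided after unblinding.

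**Working it through.** **Does any other text supply the contrast?** SAP 7.A says that groups will be compared statistically in Phase I, but it stands under the efficacy objectives, and SAP Table 6 lists no cognitive measure among the outcomes. SAP 8.E and 8.J cover suicidality and hearing only. The gap is therefore not filled elsewhere.

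**Is there a figure to reproduce?** No. The documents give no retest gain, baseline correlation, margin or power for cognition. What follows is an illustration.

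**Inputs.** From the documents: 50 per arm (Protocol, Study Summary) and the two-sided 5% level (Protocol 15.2, stated for the efficacy analyses). Assumed: correlation r between baseline and Week 6 of 0.5 to 0.8 (0.6 to 0.8 in the scenarios), and retest gain or session dip as stated. The unit is one SD of the score, all 50 per arm complete, and one test is considered at a time.

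**Formulas** (normal approximation):

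- SE of mean change in the active arm = sqrt(2(1−r)/50)
- SE of the baseline-adjusted active-sham difference = sqrt((2/50)(1−r²))
- 95% CI half-width of that difference = 1.96 × SE
- difference detectable with 80% power = (1.96 + 0.84) × SE

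| r | SE, change in active arm | SE, active-sham | Half-width | Detectable, 80% power |
|---|---|---|---|---|
| 0.5 | 0.141 | 0.173 | 0.34 | 0.48 |
| 0.6 | 0.126 | 0.160 | 0.31 | 0.45 |
| 0.7 | 0.110 | 0.143 | 0.28 | 0.40 |
| 0.8 | 0.089 | 0.120 | 0.24 | 0.34 |

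**Scenarios.** The probability that a within-arm test shows a significant decline is Φ(−m/SE − 1.96), where m is the mean change; for an improvement it is Φ(m/SE − 1.96). The power of the adjusted comparison for a true difference d is Φ(d/SE − 1.96).

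| Truth | Within-arm result | r=0.6 | r=0.7 | r=0.8 | Active-sham test, r=0.6 / 0.7 / 0.8 |
|---|---|---|---|---|---|
| Loss 0.3, retest gain 0.3 | decline flagged | 2.5% | 2.5% | 2.5% | 47% / 56% / 71% |
| Loss 0.5, retest gain 0.5 | decline flagged | 2.5% | 2.5% | 2.5% | 88% / 94% / 99% |
| No TMS effect, retest gain 0.3 | improvement flagged | 66% | 78% | 92% | 5% |
| No TMS effect, dip of 0.2 in both arms | decline flagged | 35% | 45% | 61% | 5% |

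Worked case, r = 0.6. With a loss of 0.3 and a gain of 0.3, m = 0, so the within-arm result is Φ(−1.96) = 2.5%. The adjusted comparison gives Φ(0.3/0.160 − 1.96) = Φ(−0.085) = 47%.

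**The case against.** **A reader might infer that the plan excludes a comparison with sham, or judges cognition against baseline in every phase.** The documents do not support this. The sentence in 15.2 fixes which time points are compared. It does not say that the arms are pooled, it does not forbid display by arm, and for later phases it also names the end of the previous phase. The caption of the cognitive table in SAP 8.G did not survive in the text available, and SAP Table 10 carries its by-group instruction in its caption. Layout by arm therefore cannot be ruled out. What stands is that no contrast is pre-specified.

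**A reader might infer that sham subjects share everything except stimulation.** They do not. The trial expects an effect of 0.50 to 0.60 on depression (Protocol 15.1), so any cognitive gain from better mood may be larger in the active arm. In the adult trial in Protocol Table 1, application site pain was 35.8% on active and 3.8% on sham, and muscle twitching 20.6% and 3.2%. Discomfort after a session may therefore also differ by arm.

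**A reader might infer that testing follows immediately on a session.** Footnote e gives no interval, and footnote c allows subjects who stop early up to two days.

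**The sizes are assumed.** This is correct. That a loss equal to the retest gain shows as no change is arithmetic, not evidence that such a gain exists.

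**The stakes may be modest.** Protocol 8.1 reports no negative cognitive effects in adult studies, the plan sets no cognitive decision rule, and the data are collected in both arms, so the contrast remains recoverable. This limits the severity, but it does not replace pre-specification.

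**Conclusion.** The concern holds as a gap in pre-specification. The stated Phase I comparison cannot separate an effect of TMS from change common to both arms, and the randomised contrast that removes such change is not specified for cognition, although it is for hearing.

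With 50 per arm completing and r of 0.5 to 0.8 (assumed), each active-sham difference would carry a 95% CI of about ±0.24 to ±0.34 SD. Losses larger than about a quarter to a third of an SD could be excluded only if the observed difference is near zero. Dropout would widen the interval, and the figures ignore multiplicity over eight tests. Power of 47% to 71% for a 0.3 SD loss favours reporting estimates with intervals over reliance on significance.

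The contrast estimates the net effect of assignment to active TMS. It includes any cognitive benefit of greater mood improvement and any discomfort specific to active sessions, and it cannot tell a transient after-effect from a lasting one. The plan should be changed, but the gap does not touch the primary efficacy claim.

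**What to change.** In SAP 8.G and Protocol 15.2, before unblinding:

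1. Name one score per test. Seven of the eight tests list several outputs; the age-adjusted scale score would serve for these, and the raw score for the Rey test.
2. For Phase I, specify an ANCOVA of the Week 6 score on treatment, baseline score and test platform, where platform records whether the subject was tested on desktop, tablet or one of each.
3. Report the active-sham difference with its 95% CI for each test as the main cognitive safety result, and say how eight intervals will be read together.
4. Keep change from baseline and from the previous phase as description, and for Phases II and III, where there is no randomised control.
5. State the limits given in the verdict.

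The cost is eight models, a choice of score and a platform variable: a small amount of extra analysis and no new data.
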